1. History of cardiovascular disease (e.g., coronary artery disease or heart failure). Ascertainment: Patient Report, EKG at Intake.

a) Remote **and hybrid** participants: Results provided of an abnormal EKG done within 6 months prior to starting the study or failure to provide an EKG done within 6 months prior to starting the study.

2. History of seizure disorder, abnormal EEGs, traumatic brain injury, renal disease (e.g. nephritis), diabetes mellitus, hypothyroidism and/or psychosis. History of active liver disease, including chronic active hepatitis, viral hepatitis (hepatitis B, C and CMV), cholestatic jaundice of any etiology, cirrhosis, toxic hepatitis, or cholestatic hepatitis or jaundice with bilirubin greater than 2.0 X upper institutional limit. Given that disulfiram may exacerbate these pre-existing conditions, patients with these conditions will be excluded. Also excluded will be individuals with a documented history of large fiber neuropathy based on EMG and/or Nerve Conduction Studies. Ascertainment: self-report, MINI and LFTs (AST & ALT) & Bilirubin not greater than 2 times upper limit at intake.

3. History of Substance Use Disorder (e.g., alcohol abuse, multi-drug dependence) within the past 2 years Ascertainment: self-report and MINI interview

4. History in the last 6 months of heavy alcohol use which is defined as binge drinking more than 5 days in a one-month period. A binge-drinking episode refers to the consumption of 5 or more drinks for men or 4 or more drinks for women in a 2-hour period

Ascertainment: alcohol use questions in the screening questionnaire (self-report).

5. Evidence of current active tick-borne illness other than Lyme disease Ascertainment: self-report and review of provided medical records

(Note: patients with evidence of positive antibodies for another TBI will be eligible unless there is evidence that this other TBI is currently active (eg., elevated LFTS (AST & ALT not greater than 2 times upper limit), low platelets, low WBC, high fevers)

6. Unwillingness to confirm that he/she will abstain from alcohol and products that may contain alcohol (including sauces, cough syrup, vinegar, backrub products, aftershave lotions) during the month prior to randomization, during the course of this study, and for 6 weeks after the last dose of study medication. (Patient Report and Urinalysis).

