On the intake day of the study, the nature of the research evaluation protocol, including potential risks and benefits, will be explained verbally to all potential subjects by an experienced member of the study team who is knowledgeable about all aspects of the evaluation process. Participants will be asked to also read the study Consent and HIPPA Forms. The person obtaining consent will answer any questions the subject may have. Once he/she feels confident the subject understands the evaluation description, he/she will obtain informed consent from the subject by having him/her sign the consent form. Participants will be verbally reminded of the key points of the consent form and procedures of the evaluation at the beginning of each study visit.

The study clinician will have a detailed and frank discussion about participants' cannabis and alcohol use and the risks of using these substances while taking disulfiram. The study clinician will also inquire if the patient is either vegan or lactose intolerant. If the patient reports being either of the two, then the pharmacy will be informed about the specific dietary restriction immediately following the intake visit. Documentation of this discussion and participants plan for not using these substances will be made in the consent procedure note.

Physical examination, sensory testing and collection of biological samples

A medical history and physical examination will be conducted, including sensory testing (pain, sound, vibration, sweat gland function). The Neuropathy Total Symptom Scale- 6 and the Total Neuropathy Scale will be administered by the clinician during the neurologic assessment at intake and at week 8. EKG will be conducted by one of the study RAs and read by one of the study clinicians in order to confirm the participants' inclusion/exclusion criteria during the intake visit.

The following tests will be performed during the study:

• CBC, Chemistry Screen, TFT (Tests performed at Nathan Klein Clinic- CBC and Chem screen with LFTS will be conducted at intake, baseline, wk 1 (post tx), 2, 4, 6, 8, and 10, study while TFTs will be done only at intake, Tox Screen will be done at Intake and Wks 2 and 6)

• Lyme, Babesia Microti (Tests performed only at intake)

• Lyme Urine Proteome Test (Test performed by the Center for Applied Proteomics and Molecular Medicine at George Mason University.- done at intake and Week 10)

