• A patient will be discontinued from treatment early if he/she shows signs of liver toxicity on laboratory tests; an abnormal finding (e.g., Moderate or Severe ALT elevation > 2x ULN or AlkPhos > 1.5x ULN or Bili > 1.5x ULN) will lead to a discontinuation of the treatment, repeat of the lab test with close monitoring of the patient, and a referral for the patient to see their internist for further liver monitoring. If patients experience any mild ALT elevation or Alk Phos elevation (e.g., ALT >ULN but <2x ULN or ALK Phos >ULN <1.5x ULN), then the study clinician will keep their disulfiram dose the same and repeat testing in 2 weeks as long as their TB remains <1.5 ULN. Patients will be advised to immediately notify their study clinician of any early symptoms of hepatitis, such as fatigue, weakness, malaise, anorexia, nausea, vomiting, jaundice or dark urine; this will lead to a medical evaluation to rule out liver involvement.

• Patients will also be discontinued from the treatment component of the study early if they experience any new onset adverse neurological reactions thought to be due to the study treatment and which persists for at least 1 week (e.g., polyneuritis, peripheral neuropathy).

Clinically, early discontinuation from treatment will occur if:

a. a patient's self-report on the CGI Global Change scale indicates a score of "very much worse" for 2 consecutive weeks or "much worse" for 4 consecutive weeks.

b. a patient's score on the BDI item 9 suicide item is 2 or higher for 2 consecutive assessments. A BDI item 9 score of 2 or 3 will lead to an evaluation by a psychiatrist and closer monitoring which will include a reassessment one week later. If the worsening suicidal ideation continues, the patient will be withdrawn from the study and appropriate clinical care will be arranged.

Blood and other Biological Samples

Please create or insert a table describing the proposed collection of blood or other biological specimens

IN-PERSON PARTICIPANT SPECIMEN COLLECTION:

The following will be drawn or collected for in-person participants:

Intake

- CBC, Chemistry Screen, TFT (Tests performed at NKI)
- 1. CBC- 1 4cc EDTA
- 2. TFTs and Chemistry Screen- 2, 8cc Red Top
- 3. Tox Screen and Pregnancy Test- 50 cc Urine

Lyme and Babesia test (Tests performed at MDL) 1. 2, 8.5cc Serum Tube

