There are some risks associated with travel during the COVID-19 pandemic for participants completing study procedures remotely or via the hybrid protocol. The number of laboratory assessments and in-person assessments has been reduced to minimize risk. Nonetheless, for safety-related reasons, it will still be necessary for participants to attend some assessments in-person.

Describe procedures for minimizing risks

Treatment with Disulfiram

1. Disulfiram-alcohol reaction. Patients are required to be alcohol-free during this study and for at least 2 weeks prior to starting the study and for 6 weeks after receiving the last dose of study medication (I.e from weeks 8-14). The consent form will describe this reaction so that patients will be aware of the typical symptom profile should he/she inadvertently consume an alcohol-containing product; this will also be described in detail to the patient by the study clinician. Patients will also be advised to check labels of all consumed products to ensure there is no alcohol within the food preparation (e.g., sauces, vinegar, cough medication).

2. Patients will be monitored for side-effects of the medication during the clinic visits and weekly phone check-ups. The number of pills taken (either 2 or 1 or none) each day can be adjusted based on tolerability

and clinician's judgment. Intolerable side effects or clinically severe worsening that is sustained for 2 consecutive assessments will result in withdrawal from the study.

3. To reduce the risk of rare but serious adverse effects, patients will be excluded from enrollment in the study if there is:

- a. Liver: evidence or history of liver disease or insufficiency
- b. Psychiatric: a lifetime history of psychosis or of bipolar disorder or recent or current suicidality
- c. Substance use: alcohol or substance abuse disorder within the past 2 years
- d. Neurologic: a lifetime history of seizures or history of abnormal EEG
- e. Cardiac: a current or lifetime history of coronary artery disease or heart failure.

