As additional precaution against liver injury, patients will be monitored closely during the study, including blood tests at intake and after weeks 2, 4, 6, and 10. If the clinician notices mild ALT or Alk Phos elevation (e.g., ALT >ULN but <2x ULN or ALK Phos >ULN <1.5x ULN), then the patient will remain at the same dose and repeat testing in 2 weeks (as long as TB <1.5 ULN). If the clinician notices moderate or severe LFT elevation (e.g., ALT > 2x ULN or AlkPhos > 1.5x ULN or Bili > 1.5x ULN), then the patient will discontinue disulfiram, be monitored closely, and referred to their internist for further liver monitoring. The clinician will also monitor the patient for signs of hepatitis, such as fatigue, weakness, anorexia, nausea, vomiting, jaundice, malaise, and dark urine.

Because disulfiram may exacerbate certain conditions, patients will be excluded from participation who have a diagnosis of diabetes mellitus, hypothyroidism, seizure disorder, cerebral damage, cardiac, liver or renal disease

4. Drug interactions:

a. Patients will be warned not to take metronidazole or paraldehyde; as the latter is not available in the United States, we anticipate this to be an unlikely risk.

b. Patients will be advised to review all new medications (prescribed or over the counter) with his/her research clinician to ensure lack of drug interactions.

Self- Report Questionnaires

Patients will be told that they can skip questions if they are too distressing to complete.

Blood Draw (These procedures will be minimally conducted as needed at NYSPI due to COVID-19.) Gloves will be used to reduce risk of infection and the skin is wiped with alcohol prior to the blood draw; if an infection occurs, it will be treated.

Sensory Testing (These procedures will not be conducted at NYSPI at present due to COVID-19.) Some participants might find the sensory testing mildly unpleasant. There is no significant risk to subjects associated with this kind of testing. The experimenter can stop the task at any time if the participant experiences discomfort and wants to discontinue the task.

Remote and hybrid participation during COVID-19 pandemic:

The number of laboratory assessments and in-person assessments has been reduced to minimize risk. However, for safety-related reasons, participants will be required to attend some assessments in-person. To

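### The bilirubin limit for entry (2x ULN) is looser than the limit for stopping (1.5x ULN), so a person can be enrolled and dosed while already over the stopping limit

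*Combined protocol and SAP*

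**What the plan says.** **Entry.** Under Inclusion/Exclusion Criteria, exclusion item 2 ends with its method of ascertainment: self-report, the MINI, and "LFTs (AST & ALT) & Bilirubin not greater than 2 times upper limit at intake". The same item and limit appear in the list for the Highly Probable group. Earlier in item 2, within the history of active liver disease, is "cholestatic hepatitis or jaundice with bilirubin greater than 2.0 X upper institutional limit". Item 2 gives no limit for alkaline phosphatase.

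**Stopping.** Criteria for Early Discontinuation gives examples of abnormal liver findings, the last of which reads "Bili > 1.5x ULN) will lead to a discontinuation of the treatment". A patient with only a mild ALT or alkaline phosphatase rise is handled differently: the clinician will "keep their disulfiram dose the same and repeat testing in 2 weeks as long as their TB remains <1.5 ULN". The section on procedures for minimizing risks repeats the limits ("ALT > 2x ULN or AlkPhos > 1.5x ULN or Bili > 1.5x ULN") and the action: "the patient will discontinue disulfiram, be monitored closely, and referred to their internist for further liver monitoring".

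**General liver exclusion.** The same risk section excludes anyone with "evidence or history of liver disease or insufficiency", without a number.

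**Testing.** For in-person participants, chemistry with "LFTS will be conducted at intake, baseline, wk 1 (post tx), 2, 4, 6, 8, and 10". For remote and hybrid participants, the Study Procedures text lists intake and weeks 2, 4, 6 and 10 only.

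**The concern.** An entry limit should be no looser than the stopping limit for the same test, unless stopping is judged against the patient's own starting value. Here it is looser for bilirubin, and nothing in the text ties the stop to the intake value.

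Followed as written, a person in the gap is exposed to a drug for which the protocol itself reports hepatic failure, and is then withdrawn although nothing has changed since intake. That withdrawal enters the drop-out rate under secondary goal 3. If it is also recorded as an adverse event, it enters the safety tables under primary aim 1. In a small pilot whose first aim is safety, a stop caused by an entry value should not be read as an effect of the drug.

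**Working it through.** The plan states no figure to reproduce. The check sets the entry and stopping limits side by side and looks for values that satisfy both.

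| Test | Eligible at intake (exclusion item 2, both lists) | Treatment stops (early discontinuation; risk minimisation) | Eligible but already over the stop |
|---|---|---|---|
| ALT | up to 2x ULN | above 2x ULN | none |
| Bilirubin | up to 2x ULN | above 1.5x ULN | above 1.5x, up to 2.0x ULN |
| Alkaline phosphatase | no limit given | above 1.5x ULN | anything above 1.5x ULN |

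1. **Bilirubin.** The band is 2.0 − 1.5 = 0.5x ULN wide. Take a person at 1.8x ULN with normal transaminases and no liver disease: 1.8 ≤ 2.0, so entry is allowed; 1.8 > 1.5, so the stopping limit is already exceeded.

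2. **Other entry text.** The jaundice-history clause also uses 2.0x and so sets no tighter limit. The general liver exclusion would remove someone judged to have liver disease or insufficiency, but no text says that bilirubin between 1.5x and 2.0x is by itself evidence of that. I found no tighter bilirubin limit at intake or baseline.

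3. **When a stable value would be seen again.** Remote and hybrid participants have no liver panel between intake and week 2, so they would be dosed before the next result. In-person participants have a baseline panel, but the Treatment Phase text has them take the first dose at that visit, and the available text does not require the result first. The visit checklists named in the protocol were not available, so this point on in-person participants is less firm.

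4. **Alkaline phosphatase.** The gap has no upper bound in item 2. I assume that the intake chemistry screen includes this test, since the stopping rule relies on it on treatment.

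5. **After the change.** With entry at or below 1.5x ULN and the stop above 1.5x ULN, no value satisfies both, for bilirubin or for alkaline phosphatase.

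**The case against.** The strongest reply is that the stopping rule addresses signs of liver toxicity and gives its multiples only as examples. A clinician who knows that an isolated value was present at intake and has not moved need not call it toxicity. A cautious clinician could equally refuse entry under the general liver exclusion. Either way few people are affected.

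This stands as a limit on size, but it does not remove the conflict. In both places the action at the stated multiple is worded as something that will happen. If clinicians override it for some patients, the liver stopping rule is applied unevenly. If they rely on the general exclusion, the 2x entry limit is not the limit actually used.

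It is also fair to say that enrolment is closed, so a new entry limit cannot change this trial.

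A reader might infer that such stops explain the drop-out problem, because the progress report gives unexpectedly frequent adverse-event drop-outs as one reason for ending enrolment. The documents do not support this: no available text mentions a stop for bilirubin or any other liver test. A reader might also infer bias in the fatigue or quality-of-life comparison. That is not supported either. Both arms follow the same disulfiram schedule in weeks 1 to 4, when a stable raised value would be found, and week 10 assessments are still sought after early discontinuation.

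**Conclusion.** The safety thresholds are inconsistent as written. The gap is isolated bilirubin above 1.5x and up to 2.0x ULN in a person not judged to have liver disease, together with any alkaline phosphatase above 1.5x ULN at intake. That the limits conflict is certain, since it follows from the text alone.

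The consequence is small and may be nil: the documents do not show that any of the 11 participants fell in the gap. It rests on two assumptions, that clinicians apply the stated multiples as written and that a value in the gap is not itself taken as evidence of liver disease. The point is worth considering before the protocol is reused. It is not a challenge to the trial's findings.

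**What to change.** **For follow-on use of the protocol.** In the ascertainment clause of exclusion item 2, in both lists, write: *AST and ALT not greater than 2 times, and bilirubin and alkaline phosphatase not greater than 1.5 times, the upper limit at intake.* The jaundice-history clause can stay, because it describes a past diagnosis and not the intake laboratory limit.

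The cost is one line in each list and the exclusion of a few people with mildly raised values. Judging the stop against the intake value would keep those people in, but it would loosen a liver safety limit, so the tighter entry limit is preferable.

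**For the existing data.** If any participant was stopped for bilirubin, report the intake value beside the on-treatment value. Describe the stop as not treatment-emergent only if the value had not risen from intake. An intake value above 1.5x ULN is not enough on its own, because a further rise on disulfiram is a safety signal. In every case keep the stop in the discontinuation count. The cost is one look-up of values already collected.

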The study clinician will have a detailed and frank discussion about participants' cannabis and alcohol use and the risks of using these substances while taking disulfiram. The study clinician will also inquire if the patient is either vegan or lactose intolerant. If the patient reports being either of the two, then the pharmacy will be informed about the specific dietary restriction immediately following the intake visit. Documentation of this discussion and participants plan for not using these substances will be made in the consent procedure note.

Physical examination

A medical history will be conducted via telehealth by a study clinician and a physical examination will be conducted by each participant's local physician. The Neuropathy Total Symptom Scale- 6 and the Total Neuropathy Scale will be administered by the local clinician during the neurologic assessment at intake and at week 8. The results of these assessments and any visit notes will be securely faxed from the local physician's office to the study clinician.

Remote participants will be required to visit their local Quest Diagnostic testing site for the following tests that will be performed during the study:

• CBC, Chemistry Screen, TFT (Tests performed at Quest Diagnostic- CBC and Chem screen with LFTS will be conducted at intake, Weeks **2**, 4, 6, and 10, study while TFTs will be done only at intake, Tox Screen will be done at Intake and Week 6)

• Lyme, Babesia Microti (Tests performed only at intake)

• Lyme Urine Proteome Test (Test performed by the Center for Applied Proteomics and Molecular Medicine at George Mason University.- samples collected at home and sent to collaborating lab at intake and Week 10)

• Fecal matter samples collected at home at intake, week 4, week 8 and at week 10 will be sent to our collaborator [name] at Northeastern University

• All females who are post-menarche and pre-menopausal will be required to take a urine pregnancy test at the time of the intake (Test performed at Quest Diagnostic)

The results of these laboratory tests will be accessible to the study clinicians via a HIPPA compliant, secure EHR portal provided by Quest Diagnostics.

HYBRID INTAKE, BASELINE, AND STUDY VISITS- (please see attached study overview visit checklist document for visit breakdown)

Informed Consent and HIPPA Forms

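### Entry limits for bilirubin and alkaline phosphatase are looser than the liver stopping limits, so a participant could be enrolled while already meeting the stopping rule

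*Combined protocol and SAP*

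**What the plan says.** **Entry.** Exclusion item 2 appears in identical form under Inclusion/Exclusion Criteria and under the second list for Highly Probable cases. Its ascertainment clause reads "LFTs (AST & ALT) & Bilirubin not greater than 2 times upper limit at intake". The body of the same item also gives a 2.0x limit for bilirubin. Neither place gives a figure for alkaline phosphatase. The section on minimizing risks adds a general exclusion for evidence or history of liver disease or insufficiency, without numbers.

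**Stopping.** Criteria for Early Discontinuation applies when a patient "shows signs of liver toxicity on laboratory tests" and gives these limits: "ALT elevation > 2x ULN or AlkPhos > 1.5x ULN or Bili > 1.5x ULN) will lead to a discontinuation of the treatment". The section on minimizing risks repeats them: "ALT > 2x ULN or AlkPhos > 1.5x ULN or Bili > 1.5x ULN), then the patient will discontinue disulfiram". Neither place mentions the intake or baseline value. Mild elevations of ALT or alkaline phosphatase lead to the same dose and a retest in two weeks, but only "as long as their TB remains <1.5 ULN".

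**Test schedule.** For in-person participants, "CBC and Chem screen with LFTS will be conducted at intake, baseline, wk 1 (post tx), 2, 4, 6, 8, and 10". For remote participants the entry begins "CBC and Chem screen with LFTS will be conducted at intake, Weeks" and continues with 2, 4, 6 and 10; hybrid participants have the same weeks. The section on minimizing risks gives the same sparser schedule: "including blood tests at intake and after weeks 2, 4, 6, and 10".

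**The concern.** A stopping rule for liver toxicity is meant to detect a change caused by the drug. If the entry criteria accept values beyond the stopping limit, the rule can fire on a value that was there before the first dose, and the protocol then describes that result as a sign of liver toxicity.

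Two things are at stake. A participant could be exposed to disulfiram when the protocol's own rule says treatment at that value should stop. The stop would also count in treatment drop-out, which is secondary goal 3, and would colour the tolerability findings under primary aim 1. The continuing-review section lists higher-than-expected drop-out from adverse events first among its reasons for ending enrollment, so the cause of each stop matters to how the pilot is read. The SAP analysis for primary aim 1 tabulates adverse events and does not ask for intake laboratory values to be shown beside a stop.

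**Working it through.** The plan states no figure to reproduce. The check sets the limits side by side and then counts the doses taken before the first listed on-treatment test.

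**1. Limits in multiples of ULN** (entry from exclusion item 2; stopping from Criteria for Early Discontinuation and the section on minimizing risks)

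| Test | Accepted at intake | Treatment stops | Accepted at entry and already a stopping value |
|---|---|---|---|
| ALT | up to 2x | above 2x | none |
| Bilirubin | up to 2x | above 1.5x | above 1.5x, up to 2x |
| Alkaline phosphatase | no number stated | above 1.5x | above 1.5x, no numeric upper bound |
| AST | up to 2x | no limit listed | not applicable |

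ALT is aligned, so the mismatch is confined to bilirubin and alkaline phosphatase.

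**2. Does the mild-elevation route rescue either case?** No. For alkaline phosphatase that route ends at 1.5x ULN. For any participant it requires bilirubin below 1.5x ULN. Both overlap cases fall outside it.

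**3. When would an unchanged value be seen?** In-person participants have liver tests at baseline and week 1. The remote and hybrid specimen lists contain no chemistry at baseline, so their first listed test after intake is at week 2.

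**4. Exposure before that test** (Treatment Phase schedule; the first dose is taken at the baseline visit)
- Week 1, 250 mg every other day, taken on days 1, 3, 5 and 7: 4 doses.
- Week 2, 250 mg daily: 7 doses.
- Total: 4 + 7 = 11 doses; 11 x 250 mg = 2,750 mg.

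This is a maximum. An earlier blood draw or a dose reduction would lower it. Every remote or hybrid participant on schedule has this exposure. It shows how late the conflict could surface and does not measure how often it would.

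**5. Scale of one case.** The SAP gives a final sample size of 11. One such stop would be 1/11 = 9.1% of those enrolled. This is a unit of scale, not an estimate. The documents give no intake laboratory values, so the number of cases is unknown and may be zero.

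**6. After the change proposed below.** With intake limits of 1.5x ULN for bilirubin and alkaline phosphatase and stopping above 1.5x ULN, no value is both accepted and already a stopping value.

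**The case against.** The strongest reply is that neither rule is purely mechanical. At entry, the clinician may exclude on evidence of liver disease, and an abnormal intake chemistry can be such evidence; item 2 also bars cholestatic jaundice of any cause. At stopping, the limits are introduced as examples, the test is repeated, and the clinician holds the intake result in every participation format. A stopping limit tighter than the entry limit also errs towards safety.

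Much of this stands. It rules out the flat reading that anyone in the overlap is eligible; the text supports only that such a person could be enrolled. It does not remove the conflict. The qualitative exclusion carries no number, while item 2 gives a numeric test that bilirubin up to 2x passes. On the stopping side, both sections say that treatment will stop.

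A reader might also infer three stronger things:

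- **That the overlap explains the drop-out reported for this trial.** The documents report no liver-rule stop and no out-of-range intake value.
- **That the comparison of schedules is biased.** Both groups follow the same dosing through week 4, and an unchanged intake value would be met at the first test, in week 1 or 2. Such stops have no systematic link to the assigned group. Stopped participants are also asked back at week 10, so outcome data need not be lost.
- **That exposure before the week 2 test is 12 doses.** Subtracting the 14 days of weeks 3 and 4 from the stated 26 treatment days gives 12, but that needs five dosing days in week 1. Alternate-day dosing allows at most four.

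**Conclusion.** The concern holds, as a minor point. As written, the limits allow someone to be enrolled with bilirubin above 1.5x and up to 2x ULN, or alkaline phosphatase above 1.5x ULN, and then be stopped for a value present before dosing. This assumes that the clinician does not use the unnumbered liver exclusion and applies the listed stopping limits as printed.

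The consequence is limited to overall tolerability and drop-out. In remote and hybrid participation the conflict might not surface until up to 11 doses (2,750 mg) had been taken. The frequency cannot be estimated from the documents. They support neither a claim that any of the 11 was affected nor a claim that the trial's findings are unsound. Because intake chemistry is collected in every format, a pre-existing value can be told apart from a drug effect once someone looks.

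**What to change.** **Any reuse of the protocol.** In exclusion item 2 of both lists, make two edits:

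- Reword the ascertainment clause to: *AST and ALT not greater than 2 times, and bilirubin and alkaline phosphatase not greater than 1.5 times, the upper limit at intake*.
- Change the 2.0x bilirubin figure in the body of the same item to 1.5x. Otherwise the item would carry two bilirubin limits.

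That is four small edits, at the price of losing a few candidates. A stopping rule defined relative to the intake value would also remove the conflict without losing candidates, but would let treatment continue at higher absolute values. Under the recommended wording, someone just below 1.5x at intake could still cross it by chance, so the intake value should be shown beside any stop. AST would still have an entry limit and no listed stopping limit; this change does not address that.

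**This trial (reporting only).** Leave unchanged the criteria under which the 11 entered. Check their intake bilirubin and alkaline phosphatase as multiples of ULN, show the intake value beside any liver-rule stop, and state in one sentence whether any stop had an intake value already above the stopping limit. The cost is a review of 11 existing results and one sentence in the report.
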